Title: ASPIRE - Aspirin to Prevent Preeclampsia in Women with Elevated Blood Pressure and Stage 1 Hypertension

Date: 12/08/2021

Clinicaltrials.gov ID: NCT04402385

Document: Protocol w SAP

HRP-503B – BIOMEDICAL RESEARCH PROTOCOL
(2017-1)

Protocol Title: ASPIRE - Aspirin to Prevent Preeclampsia in Women with Elevated Blood Pressure and Stage 1 Hypertension

Principal Investigator: [name]

Sub-Investigators: [name]; [name], MSCI; [name], MPH

Version Date: 12/08/2021

Clinicaltrials.gov Registration #: NCT04402385

SECTION I: RESEARCH PLAN

1. **Statement of Purpose:** State the scientific aim(s) of the study, or the hypotheses to be tested.
To determine if low dose aspirin reduces the incidence of hypertensive disorders of pregnancy (gestational hypertension, preeclampsia, eclampsia, and HELLP syndrome) in pregnant women with stage 1 hypertension and elevated blood pressure.
2. **Probable Duration of Project:** State the expected duration of the project, including all follow-up and data analysis activities.
5 years
3. **Background:** Describe the background information that led to the plan for this project. Provide references to support the expectation of obtaining useful scientific data.

New hypertension guidelines proposed in 2017 by the American College of Cardiology/ American Heart Association (ACC/AHA) redefined blood pressure (BP) categories as Stage 1 hypertension (systolic 130-139 mmHg or diastolic 80-89 mmHg), Elevated (systolic 120-129 mmHg and diastolic <80mm) and Normal (<120/<80 mmHg). Adaption of these new definitions increases the prevalence of hypertension among adults in the United States by approximately 31 million people. Since publication of the updated guidelines, several studies have assessed lower levels of blood pressure elevations and subsequent pregnancy outcomes.

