6. Delivery records will be abstracted for outcomes listed below. Neonatal records will be reviewed from birth until 1 year of age. Neonatal and infant chart abstraction will include birthweight, Apgar scores, hospital course, problem visit, diagnoses, medications, emergency department visits, and hospitalizations. Participant's postpartum course will be reviewed for 1 year postpartum, including outpatient visits, emergency department visits, and any hospitalizations.

The study will be performed by an intent-to-treat analysis. Thus, even women who discontinue study medication will be included in final analyses.

5. Genetic Testing N/A 6. **Subject Population:** Provide a detailed description of the types of human subjects who will be recruited into this study.

Pregnant women ages ≥ 18 years with live, singleton pregnancies enrolled prior to 20 weeks gestational age. These women will receive prenatal care through a Yale New Haven Hospital (YNHH)-associated obstetric and/or midwifery practice. They will plan to deliver at a hospital within the YNHH system.

7. **Subject classification:** Check off all classifications of subjects that will be specifically recruited for enrollment in the research project. Will subjects who may require additional safeguards or other considerations be enrolled in the study? If so, identify the population of subjects requiring special safeguards and provide a justification for their involvement.

 Children	 Healthy	 Fetal material, placenta, or dead fetus
 Non-English Speaking	 Prisoners	 Economically disadvantaged persons
 Decisionally Impaired	 Employees	 Pregnant women and/or fetuses
 Yale Students	 Females of childbearing potential	

NOTE: Is this research proposal designed to enroll children who are wards of the state as potential subjects?

Yes No 8. **Inclusion/Exclusion Criteria:** What are the criteria used to determine subject inclusion or exclusion?**Inclusion:**

- Age ≥ 18 years
- Singleton pregnancy

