These UPIRSOs/SAEs will be reported to the IRB in accordance with IRB Policy 710, using the appropriate forms found on the website. All related events involving risk but not meeting the prompt reporting requirements described in IRB Policy 710 should be reported to the IRB in summary form at the time of continuing review. If appropriate, such summary may be a simple brief statement that events have occurred at the expected frequency and level of severity as previously documented. In lieu of a summary of external events, a current DSMB report can be submitted for research studies that are subject to oversight by a DSMB (or other monitoring entity that is monitoring the study on behalf of an industry sponsor).

7. Plan for reporting adverse events to co-investigators on the study, as appropriate the protocol's research monitor(s), e.g., industrial sponsor, Yale Cancer Center Data and Safety Monitoring Committee (DSMC), Protocol Review Committee (PRC), DSMBs, study sponsors, funding and regulatory agencies, and regulatory and decision-making bodies.

For the current study, the following individuals, funding, and/or regulatory agencies will be notified:

- *All Co-Investigators listed on the protocol.*
- *Yale IRB*
- *Independent Data Safety Monitoring Board*
- *Yale Investigational Drug Services*
- *National Institutes of Health*

The principal investigator and [name] will conduct a review of all adverse events upon completion of every study subject. The principal investigator and [name] will evaluate the frequency and severity of the adverse events and determine if modifications to the protocol or consent form are required.

d. For multi-site studies for which the Yale PI serves as the lead investigator: N/A

13. Statistical Considerations: Describe the statistical analyses that support the study design.

Our sample size calculation is based on a secondary analysis of a Maternal-Fetal Medicine Units (MFMU) randomized controlled trial and our own retrospective analysis of YNHH data. The secondary analysis analyzed a subset of women with stage 1 hypertension randomized to aspirin 60mg daily versus placebo. In this study, the incidence of stage 1 hypertension was 19%. The incidence of preeclampsia in women with stage 1 hypertension was 39% in total. There was a 40% decrease in relative risk of developing preeclampsia in women who took aspirin 60mg daily versus placebo.

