A retrospective cohort study done at YNHH found a 29% incidence of hypertensive disorders of pregnancy in women with stage 1 hypertension. We anticipate a 40% risk reduction in the prevalence of preeclampsia from 29% in the placebo group to 18% in the aspirin group. To detect this difference with a power of 80% and $\alpha = 0.05$, we will need to randomize a total of 466 women with elevated blood pressure or stage 1 hypertension, 233 in each of the aspirin and placebo arms.

SECTION II: RESEARCH INVOLVING DRUGS, BIOLOGICS, RADIOTRACERS, PLACEBOS AND DEVICES
--

If this section (or one of its parts, A or B) is not applicable, check off N/A and delete the rest of the section.

A. RADIOTRACERS N/A

B. DRUGS/BIOLOGICS N/A

1. If an **exemption from IND filing requirements** is sought for a clinical investigation of a drug product that is lawfully marketed in the United States, review the following categories and complete the category that applies (and delete the inapplicable categories):

Exempt Category 1: The clinical investigation of a drug product that is lawfully marketed in the United States can be exempt from IND regulations if all of the following are yes:	
1. The intention of the investigation is NOT to report to the FDA as a well-controlled study in support of a new indication for use or to be used to support any other significant change in the labeling for the drug.	
2. The drug that is undergoing investigation is lawfully marketed as a prescription drug product, and the intention of the investigation is NOT to support a significant change in the advertising for the product.	
3. The investigation does NOT involve a route of administration or dosage level or use in populations or other factor that significantly increases the risks (or decreases the acceptability of the risks) associated with the use of the drug product	
2. The investigation will be conducted in compliance with the requirements for institutional (HIC) review and with the requirements for informed consent of the FDA regulations (21 CFR Part 50 and 21 CFR Part 56).	
3. The investigation will be conducted in compliance with the requirements regarding promotion and charging for investigational drugs.	

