There may be reduction in rates of hypertensive disorders of pregnancy (gestational hypertension, preeclampsia, HELLP syndrome, eclampsia) both to study participants and future pregnant women with elevated BP and stage 1 hypertension.

SECTION VI: RESEARCH ALTERNATIVES AND ECONOMIC CONSIDERATIONS

1. **Alternatives:** What other alternatives are available to the study subjects outside of the research?

If women do not want to participate in the study, they will continue routine prenatal care.

2. **Payments for Participation (Economic Considerations):** Describe any payments that will be made to subjects, the amount and schedule of payments, and the conditions for receiving this compensation.

N/A

3. **Costs for Participation (Economic Considerations):** Clearly describe the subject's costs associated with participation in the research, and the interventions or procedures of the study that will be provided at no cost to subjects.

There are no costs to study participants. Study medications (whether low dose aspirin or placebo) will be provided at no cost. No further interventions or procedures will be required.

4. **In Case of Injury:** This section is required for any research involving more than minimal risk, and for minimal risk research that presents the potential for physical harm (e.g., research involving blood draws).

a. Will medical treatment be available if research-related injury occurs?

Medical treatment will not be available from research staff.

b. Where and from whom may treatment be obtained?

Medical treatment will be through the participant's usual provider, emergency room, and any other health professionals as needed.

c. Are there any limits to the treatment being provided?

No.

d. Who will pay for this treatment?

Insurance will be billed for any treatment and the participants will be responsible for any co-pays required by the insurance company for standard treatment.

e. How will the medical treatment be accessed by subjects?

If needed, medical treatment will be sought through usual avenues—either through the patient's usual healthcare provider (whether obstetrician or primary care physician) or emergency department. Participants will be asked to report any side effects of study medication (whether aspirin or placebo). If any side effects are reported, research personnel will encourage and help set up medical diagnosis and treatment services.

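### Section 13 takes its 29% control rate from all hypertensive disorders of pregnancy and its 40% reduction from preeclampsia, so the 80% power is not supported as labelled

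*Combined protocol and SAP*

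**What the plan says.** Section I, 13 builds the sample size from two sources.

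- The effect comes from a secondary analysis of a multicentre aspirin trial: "There was a 40% decrease in relative risk of developing preeclampsia in women who took aspirin 60mg daily versus placebo". The outcome there is preeclampsia. The literature list in Section I, 3 gives the same result as a risk ratio of 0.61 (95% confidence interval 0.39 to 0.94).
- The control rate comes from the local hospital: "A retrospective cohort study done at YNHH found a 29% incidence of hypertensive disorders of pregnancy in women with stage 1 hypertension".

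The next sentence joins them: "We anticipate a 40% risk reduction in the prevalence of preeclampsia from 29% in the placebo group to 18% in the aspirin group". For 80% power at an alpha of 0.05, it concludes, "we will need to randomize a total of 466 women with elevated blood pressure or stage 1 hypertension", 233 per arm.

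Elsewhere the endpoint varies. The Statement of Purpose (Section I, 1) is "To determine if low dose aspirin reduces the incidence of hypertensive disorders of pregnancy", listing gestational hypertension, preeclampsia, eclampsia and HELLP syndrome. Section V (Potential Benefits) names the same composite. The trial title says "Aspirin to Prevent Preeclampsia in Women with Elevated Blood Pressure and Stage 1 Hypertension". Section I, 4 states "Delivery records will be abstracted for outcomes listed below", but no list follows in the public text, and no section designates a primary endpoint.

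**The concern.** Preeclampsia is one of the four components of HDP in the Statement of Purpose, so a rate for one is not a rate for the other. In two consecutive sentences the 29% changes from an HDP rate to a preeclampsia rate. The 40% is only ever reported for preeclampsia. Nowhere do the documents give 29% as a preeclampsia rate, or any aspirin effect on HDP.

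The stake is how the result will be read. With no designated primary endpoint, either outcome could later be presented as the one powered at 80%. A null result on HDP would be taken as coming from a trial with 80% power, although that figure depends on a preeclampsia effect carrying over in full to the composite. Section 13 does not say that this transfer is being made.

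A second, smaller mismatch lies in the same sentences. The 29% describes women with stage 1 hypertension only, while the 466 also include women with elevated blood pressure.

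**Working it through.** **Inputs.** Control 29%, treated 18%, alpha 0.05, power 80%, 233 per arm (Section I, 13); 1:1 allocation (Section I, 4). Sidedness is not stated. I take two-sided, because it reproduces the plan's figure and one-sided does not (366 in total).

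**Step 1: reproduce the plan.** Pooled-variance formula for two proportions, no continuity correction, with p̄ = (0.29 + 0.18)/2 = 0.235:

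n per arm = [1.960·√(2p̄(1−p̄)) + 0.842·√(p₁(1−p₁) + p₂(1−p₂))]² / (p₁−p₂)²

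= [1.960 × 0.5996 + 0.842 × 0.5946]² / 0.11² = 232.05, so 233 per arm and 466 in total. This matches.

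Power at 233 per arm = Φ{[0.11·√233 − 1.960 × 0.5996] / 0.5946} = Φ(0.847) = 80.2%.

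The implied relative reduction is 1 − 18/29 = 37.9%, not 40%. An exact 40% would give 0.6 × 29% = 17.4% and 207 per arm, so rounding to 18% is slightly conservative.

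**Step 2: read the endpoint as HDP.** The 29% has a source; the reduction does not. Same formula, 233 per arm, control 29%. The reductions below the first row are assumptions.

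| Reduction in HDP | Aspirin rate | Power |
|---|---|---|
| 37.9% (plan) | 18.0% | 80.2% |
| 35% | 18.85% | 73% |
| 30% | 20.3% | 59% |
| 25% | 21.75% | 44% |
| 20% | 23.2% | 30% |

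**Step 3: read the endpoint as preeclampsia.** The 40% has a source; the 29% does not. The documents give two preeclampsia rates for women with stage 1 hypertension on placebo.

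| Placebo rate | Where | Aspirin rate at 40% reduction | Power at 233 per arm |
|---|---|---|---|
| 15% | Section I, 3, narrative | 9% | 51% |
| 39.1% | Section I, 3, literature list | 23.46% | about 96% |

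Section 13 repeats the second rate as 39%, described as the total rather than the placebo rate.

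Neither rate transfers cleanly to this trial. The 15% is for women with pressures of 135–139 and/or 85–89, while this trial enrols from 130 and/or 80. The 39.1% is set against normotensive women at high risk, while this trial excludes the main high-risk conditions (Section I, 8; Section II, Use of Placebo). A 39% preeclampsia rate also cannot hold in the same women as a 29% HDP rate.

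**Step 4: population.** Section I, 3 reports adjusted relative risks of any HDP of 1.54 (1.18 to 2.02) for elevated blood pressure and 2.16 (1.31 to 3.57) for stage 1. The intervals overlap and the cohort was nulliparous, so these show a direction, not a usable rate. If the HDP rate is lower in women with elevated blood pressure, the control rate in the 466 falls below 29%, and power falls with it at the same relative reduction.

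**The case against.** The strongest reply is that this is one wrong word. The purpose, the expected benefit and the source of the 29% all say HDP; put HDP in place of preeclampsia and the control rate is properly sourced. Section 13 also calls the reduction anticipated, names both sources and says openly that the 40% was for preeclampsia. The smaller reductions in the table come from no source in the documents.

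Much of this stands. HDP is the likelier reading, and the fix follows it. The smaller reductions are assumptions and should be marked as such. But correcting the word does not supply an effect for HDP. It leaves the plan relying on a preeclampsia reduction for a broader outcome, without saying so or giving a reason.

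A reader might go further in two ways that the documents do not support.

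- One is that 466 is miscalculated. It is not; it reproduces exactly.
- The other is that the trial is underpowered. Nothing here shows that. If HDP falls by 38% from 29%, power is 80%. If preeclampsia is meant and the 39.1% rate applied, power would be about 96%. The direction of any error depends on the endpoint meant and on which of two conflicting rates is relevant.

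**Conclusion.** The point holds as an inconsistency in the only sample-size justification. As labelled, 80% power is attached to an endpoint whose control rate has no source; relabelled as HDP, it rests on a reduction that has no source.

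The range is wide enough to matter: from 80% down to 30% for HDP as the assumed reduction goes from 38% to 20%, and from 51% to about 96% for preeclampsia across the documents' own rates. These figures assume a two-sided test at 0.05, 233 analysed per arm, no continuity correction and, for HDP, a true control rate of 29%. They show that the claim of 80% power is unsupported as written; they do not estimate the trial's actual power.

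**What to change.** In Section I, 13:

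1. Relabel the 29% to 18% comparison as the incidence of hypertensive disorders of pregnancy. Name that composite as the single primary endpoint, to match Section I, 1, and list preeclampsia as secondary.
2. Keep 466 women and restate the power as 80% for a 38% relative reduction in HDP (29% to 18%), two-sided.
3. State that this reduction is an assumption carried over from a preeclampsia result, and give the justification for it.
4. Add power at reductions of 35%, 30%, 25% and 20% (73%, 59%, 44%, 30%), marked as assumptions.
5. State that the 29% comes from stage 1 women only and that power falls if women with elevated blood pressure have a lower rate. Give their rate from the local cohort if it holds one.
6. Reconcile the 15% and 39% preeclampsia rates with each other and with the 29% HDP rate.

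The cost is wording, one small table, a return to the cited reports and, if possible, a re-tabulation of the local cohort. No extra patients or visits are needed. The price is a less favourable statement of power: below 60% if the composite reduction is 30% or less.

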- The aspirin and placebo tablets expire after 6 months. These expiration dates are clearly labeled and discussed with the patient.

- *Unused study medication is collected at the completion of the study (after delivery of their baby) and returned to IDS*

Check applicable Investigational Drug Service utilized:

YNHH IDS CMHC Pharmacy West Haven VA

PET Center None

Other:

Note: If the YNHH IDS (or comparable service at CMHC or WHVA) will not be utilized, explain in detail how the PI will oversee these aspects of drug accountability, storage, and preparation.

2. Use of Placebo: Not applicable to this research project

If use of a placebo is planned, provide a justification which addresses the following:

- Describe the safety and efficacy of other available therapies. If there are no other available therapies, state this.
No other available therapies.
- State the maximum total length of time a participant may receive placebo while on the study.
Total length is from randomization until delivery (maximum 36 weeks). Aspirin will not be withheld from patients that would have otherwise received it as part of the standard of care were they not in this study. Women with any single high-risk factor or 2+ moderate risk factors will be offered aspirin as part of their clinical care and are not included in this study; this study only enrolls women with elevated blood pressure or stage 1 hypertension +/- only one other moderate risk factor.
- Address the greatest potential harm that may come to a participant as a result of receiving placebo.
Greatest harm would be hypersensitivity to any included ingredient in the placebo
- Describe the procedures that are in place to safeguard participants receiving placebo.
Use of Yale IDS for preparation of placebo
Data Safety Monitoring Committee will review both the aspirin and placebo arms for any adverse events

3. Continuation of Drug Therapy After Study Closure Not applicable to this project

Are subjects provided the opportunity to continue to receive the study drug(s) after the study has ended?

Yes If yes, describe the conditions under which continued access to study drug(s) may apply as well as conditions for termination of such access. *Write here*

NO If no, explain why this is acceptable.

Use of low dose aspirin is beneficial during pregnancy to reduce the risk of preeclampsia. The American College of Obstetricians and Gynecologists does not currently endorse postpartum use.

B. DEVICES

N/A

SECTION III: RECRUITMENT/CONSENT AND ASSENT PROCEDURES

1. Targeted Enrollment: Give the number of subjects:

- Targeted for enrollment at Yale for this protocol: 466
- If this is a multi-site study, give the total number of subjects targeted across all sites: N/A

2. Indicate recruitment methods below. Attach copies of any recruitment materials that will be used.

 Flyers	 Internet/web postings	 Radio
 Posters	 Mass email solicitation	 Telephone
 Letter	 Departmental/Center website	 Television
 Medical record review*	 Departmental/Center research boards	 Newspaper
 Departmental/Center newsletters	 Web-based clinical trial registries	 Clinicaltrials.gov
 YCCI Recruitment database	 Social Media (Twitter/Facebook):	
 Other:		

* Requests for medical records should be made through JDAT as described at

<http://medicine.yale.edu/ycci/oncore/availableservices/datarequests/datarequests.aspx>

3. Recruitment Procedures:

a. Describe how potential subjects will be identified.

Subjects will be identified through routine prenatal visits at Yale-associated OBGYN offices (maternal-fetal medicine office, Women's Center, Yale Health Plan, and private obstetric offices that deliver at YNHH). Blood pressures will be observed for the year preceding pregnancy and up to 20 weeks gestation through chart review.

b. Describe how potential subjects are contacted.

Subjects will be contacted in person during the time of a routine prenatal visit.

c. Who is recruiting potential subjects?

All research staff personnel. Potential subjects may also be referred to research staff by clinical staff at the above-mentioned clinic locations.

4. Assessment of Current Health Provider Relationship for HIPAA Consideration:

Does the Investigator or any member of the research team have a direct existing clinical relationship with any potential subject?

Yes, all subjects

Yes, some of the subjects

No

If yes, describe the nature of this relationship.

Primary investigator may be the physician in charge of care for a subset of these women, if they are recruited from the maternal-fetal medicine office or present to labor and delivery at Yale's York Street campus.

5. Request for waiver of HIPAA authorization: (When requesting a waiver of HIPAA Authorization for either the entire study, or for recruitment purposes only. Note: if you are collecting PHI as part of a phone or email screen, you must request a HIPAA waiver for recruitment purposes.)

Choose one:

For entire study

For recruitment/screening purposes only

For inclusion of non-English speaking subject if short form is being used and there is no translated HIPAA research authorization form available on the University's HIPAA website at hipaa.yale.edu.

i. Describe why it would be impracticable to obtain the subject's authorization for use/disclosure of this data: *We will need to review the potential subject's medical record prior to approaching her about the*

study in order to confirm that she is medically eligible. It is impractical to approach patients about the study if they are not medically eligible, given the time involved in approaching patients and the volume of patients seen at the clinics. Once we have determined initial medical eligibility, we will then screen those patients in-person to confirm all eligibility criteria has been met.

- ii. If requesting a waiver of **signed** authorization, describe why it would be impracticable to obtain the subject's signed authorization for use/disclosure of this data: N/A

The investigator assures that the protected health information for which a Waiver of Authorization has been requested will not be reused or disclosed to any person or entity other than those listed in this application, except as required by law, for authorized oversight of this research study, or as specifically approved for use in another study by an IRB.

Researchers are reminded that unauthorized disclosures of PHI to individuals outside of the Yale HIPAA-Covered entity must be accounted for in the "accounting for disclosures log", by subject name, purpose, date, recipients, and a description of information provided. Logs are to be forwarded to the Deputy HIPAA Privacy Officer.

- 6. **Process of Consent/Accent:** Describe the setting and conditions under which consent/assent will be obtained, including parental permission or surrogate permission and the steps taken to ensure subjects' independent decision-making.

The entire consent form will be reviewed with interested women who meet study inclusion criteria and do not have any exclusion criteria. The consent form will be summarized verbally by research staff personnel, with time for questions at each section of the consent form. Women will then be asked to read the consent form. Any questions or concerns will be reviewed. Women ages 18+ will be enrolled, so parental permission is not required. Women will only be included if they are English or Spanish-speaking. If another person is with the woman during her routine prenatal visit, she will be asked if she would like to discuss the study on her own or together with the accompanying person or people.

The consent form has been translated into Spanish by the Yale Center for Clinical Investigation's translation services. Spanish-speaking patients will be consented by utilizing Yale language services.

- 7. **Evaluation of Subject(s) Capacity to Provide Informed Consent/Accent:** Indicate how the personnel obtaining consent will assess the potential subject's ability and capacity to consent to the research being proposed. *Women will be assumed to have capacity to provide informed consent for research unless there is indication to the contrary. These indications include: known cognitive impairment, altered mental status, difficulties in communication observed during research staff interaction, psychotic symptoms, bizarre behavior. Women with these indications will not be included in the research study. If any of these symptoms or behaviors are new, their medical provider will be informed immediately for further assessment.*

- 8. **Non-English Speaking Subjects:** Explain provisions in place to ensure comprehension for research involving non-English speaking subjects. If enrollment of these subjects is anticipated, translated copies of all consent materials must be submitted for approval prior to use.

Spanish speakers will be included. The consent form has been translated by the Yale Center for Clinical Investigation's official translation services. Spanish speaking participants will be counseled utilizing Yale language services for all discussions and study visits.

As a limited alternative to the above requirement, will you use the short form* for consenting process if you unexpectedly encounter a non-English speaking individual interested in study participation and the translation of the long form is not possible prior to intended enrollment? YES NO

Note* If more than 2 study participants are enrolled using a short form translated into the same language, then the full consent form should be translated into that language for use the next time a subject speaking that language is to be enrolled.

Several translated short form templates are available on the HRPP website (yale.edu/hrpp) and translated HIPAA Research Authorization Forms are available on the HIPAA website (hipaa.yale.edu). If the translation of the short form is not available on our website, then the translated short form needs to be submitted to the IRB office for approval via modification prior to enrolling the subject. *Please review the guidance and presentation on use of the short form available on the HRPP website.*

If using a short form without a translated HIPAA Research Authorization Form, please request a HIPAA waiver in the section above.

9. **Consent Waiver:** In certain circumstances, the HIC may grant a waiver of signed consent, or a full waiver of consent, depending on the study. If you will request either a waiver of consent, or a waiver of signed consent for this study, complete the appropriate section below.

Not Requesting any consent waivers

SECTION IV: PROTECTION OF RESEARCH SUBJECTS

Confidentiality & Security of Data:

- What protected health information (medical information along with the HIPAA identifiers) about subjects will be collected and used for the research?
 - Past medical and surgical history, allergies, family history
 - Medication list
 - The rest of the participant's medical record held by **Yale New Haven Health** created from the start of pregnancy and up to 1 year after delivery
 - Records about phone calls made as part of this research
 - Records about study visits
 - Information obtained during this research regarding
 - Vital signs, including blood pressure
 - Physical exams
 - Laboratory, x-ray, and other test results
 - Diaries and questionnaires
 - The diagnosis and treatment of any physical or mental health condition
 - Records about any study drug received
 - Neonatal and infant records until 1 year of age
 - Information obtained during this research regarding
 - Birthweight
 - Apgar scores
 - Delivery records
 - Laboratory, x-ray, and other test results

- Diagnosis and treatment of any physical or mental health condition
- Outpatient, emergency department, and hospital visits/admissions until 1 year of age

2. How will the research data be collected, recorded and stored?

Data will be collected from the patients' medical records (including the medical record of their baby) and from self-report. It will be recorded/stored in REDCap, OnCore and on a Yale server accessible only to members of the research team. This server is on a secure, encrypted hospital-issued computer.

3. How will the digital data be stored? CD DVD Flash Drive Portable Hard Drive Secured Server Laptop Computer Desktop Computer Other

4. What methods and procedures will be used to safeguard the confidentiality and security of the identifiable study data and the storage media indicated above during and after the subject's participation in the study?

All subjects will be assigned a unique study ID code upon enrollment. Documents linking the patient to their ID code will be kept on a Yale server accessible only to members of the research team. This server is on a secure, encrypted hospital-issued computer. All data will be de-identified at the conclusion of chart review. Data analysts will have access to only de-identified information. Patient consent forms and chart abstraction forms will be kept in a locked cabinet in a locked research office at the Yale Maternal-Fetal Medicine office. This locked cabinet may only be accessed by research personnel.

All portable devices must contain encryption software, per University Policy 5100. If there is a technical reason a device cannot be encrypted please submit an exception request to the Information Security, Policy and Compliance Office by clicking on url <http://its.yale.edu/egrc> or email [contact]

5. What will be done with the data when the research is completed? Are there plans to destroy the identifiable data? If yes, describe how, by whom and when identifiers will be destroyed. If no, describe how the data and/or identifiers will be secured.

Data will remain on an encrypted server through Yale University. If research personnel leave the university, data will not travel with them.

6. If appropriate, has a Certificate of Confidentiality been obtained?

N/A

SECTION V: POTENTIAL BENEFITS

Potential Benefits: Identify any benefits that may be reasonably expected to result from the research, either to the subject(s) or to society at large. (Payment of subjects is not considered a benefit in this context of the risk benefit assessment.)

There may be reduction in rates of hypertensive disorders of pregnancy (gestational hypertension, preeclampsia, HELLP syndrome, eclampsia) both to study participants and future pregnant women with elevated BP and stage 1 hypertension.

SECTION VI: RESEARCH ALTERNATIVES AND ECONOMIC CONSIDERATIONS

1. **Alternatives:** What other alternatives are available to the study subjects outside of the research?

If women do not want to participate in the study, they will continue routine prenatal care.

2. **Payments for Participation (Economic Considerations):** Describe any payments that will be made to subjects, the amount and schedule of payments, and the conditions for receiving this compensation.

N/A

3. **Costs for Participation (Economic Considerations):** Clearly describe the subject's costs associated with participation in the research, and the interventions or procedures of the study that will be provided at no cost to subjects.

There are no costs to study participants. Study medications (whether low dose aspirin or placebo) will be provided at no cost. No further interventions or procedures will be required.

4. **In Case of Injury:** This section is required for any research involving more than minimal risk, and for minimal risk research that presents the potential for physical harm (e.g., research involving blood draws).

a. Will medical treatment be available if research-related injury occurs?

Medical treatment will not be available from research staff.

b. Where and from whom may treatment be obtained?

Medical treatment will be through the participant's usual provider, emergency room, and any other health professionals as needed.

c. Are there any limits to the treatment being provided?

No.

d. Who will pay for this treatment?

Insurance will be billed for any treatment and the participants will be responsible for any co-pays required by the insurance company for standard treatment.

e. How will the medical treatment be accessed by subjects?

If needed, medical treatment will be sought through usual avenues—either through the patient's usual healthcare provider (whether obstetrician or primary care physician) or emergency department. Participants will be asked to report any side effects of study medication (whether aspirin or placebo). If any side effects are reported, research personnel will encourage and help set up medical diagnosis and treatment services.

During the study visits (whether conducted in person or by telephone), we will ask women questions about their blood pressure and symptoms of preeclampsia. If any study participant notes onset of preeclampsia symptoms (headache, vision changes, right upper quadrant pain, and/or dyspnea) or new onset of systolic blood pressure ≥ 140 mm Hg and/or diastolic blood pressure ≥ 90 mm Hg, she will be asked to contact her primary obstetrician immediately.

IMPORTANT REMINDERS

Will this study have a billable service? Yes No

A billable service is defined as any service rendered to a study subject that, if he/she was not on a study, would normally generate a bill from either Yale-New Haven Hospital or Yale Medical Group to the patient or the patient's insurer. The service may or may not be performed by the research staff on your study, but may be provided by professionals within either Yale-New Haven Hospital or Yale Medical Group (examples include x-rays, MRIs, CT scans, specimens sent to central labs, or specimens sent to pathology). Notes: 1. There is no distinction made whether the service is paid for by the subject or their insurance (Standard of Care) or by the study's funding mechanism (Research Sponsored). 2. This generally includes new services or orders placed in EPIC for research subjects.

If answered, "yes", this study will need to be set up in OnCore, Yale's clinical research management system, for Epic to appropriately route research related charges. Please contact [contact]

Are there any procedures involved in this protocol that will be performed at YNHH or one of its affiliated entities?

Yes No

If Yes, please answer questions a through c and note instructions below.

a. Does your YNHH privilege delineation currently include the **specific procedure** that you will perform? Yes No

b. Will you be using any new equipment or equipment that you have not used in the past for this procedure? Yes No

c. Will a novel approach using existing equipment be applied? Yes No

If you answered "no" to question 4a, or "yes" to question 4b or c, please contact the YNHH Department of Physician Services ([name]) for prior approval before commencing with your research protocol.

IMPORTANT REMINDER ABOUT RESEARCH AT YNHH

Please note that if this protocol includes Yale-New Haven Hospital patients, including patients at the HRU, the Principal Investigator and any co-investigators who are physicians or mid-level practitioners (includes PAs, APRNs, psychologists and speech pathologists) who may have direct patient contact with patients on YNHH premises must have medical staff appointment and appropriate clinical privileges at YNHH. If you are uncertain whether the study personnel meet the criteria, please telephone the Physician Services Department at [contact]. **By submitting this protocol as a PI, you attest that you and any co-investigator who may have patient contact has a medical staff appointment and appropriate clinical privileges at YNHH.**
